### **6.4. Nonclinical Studies**

Nonclinical single-dose gross tolerance and toxicokinetic studies and repeat-dose toxicology and toxicokinetic studies in rats and nonhuman primates with cipaglucosidase alfa alone, miglustat alone, and co-administered cipaglucosidase alfa/miglustat did not reveal any significant or adverse treatment-related changes in a variety of parameters including body weight, food consumption, hematology, clinical chemistry, central nervous system (rats), cardiovascular (nonhuman primates), and electrocardiogram (ECG) evaluation. In addition, no treatment-related microscopic findings were detected on histologic evaluation. Notably, in the single-dose gross tolerance and toxicokinetic study of miglustat in nonhuman primates, emesis was observed following treatment at the mid and high doses of 250 and 1000 mg/kg, but was not observed at the low dose of 25 mg/kg, and food consumption was not affected. In the 13-week co-administration toxicity study of cipaglucosidase alfa/miglustat in nonhuman primates, no treatment-related emesis was observed at any dose of miglustat, including the highest tested dose of 175 mg/kg. No other overt signs of toxicity were noted in any of the single- or repeat-dose toxicity studies.

## **6.5. Clinical Studies**

Study ATB200-02 is an ongoing Phase 1/2 first-in-human study of safety, tolerability, PK, PD, and efficacy of cipaglucosidase alfa/miglustat in subjects with LOPD. The study is being conducted in 4 stages: single-ascending doses of cipaglucosidase alfa (Stage 1, 6 weeks), multiple-ascending doses of miglustat co-administered with cipaglucosidase alfa (Stage 2, 12 weeks), extended treatment at the selected doses (Stage 3, 2 years), and long-term extension (Stage 4, until approval).

Refer to the current Investigator's Brochure (IB) for updated clinical information.

## **6.6. Summary of Known and Potential Risks and Benefits**

Based on efficacy and safety information in the Investigator's Brochure, the benefit-risk balance of cipaglucosidase alfa/miglustat remains positive overall. Cipaglucosidase alfa/miglustat has demonstrated clinically significant benefits in the treatment of Pompe disease, and no important risks have been identified that would preclude the use of cipaglucosidase alfa/miglustat. Mild to moderate IARs have been identified in ongoing clinical studies and are manageable with reduction or temporary stopping of infusion and premedication with corticosteroids, antihistamines, and acetaminophen. No life-threatening or fatal IARs have been observed in clinical studies to date. As with any investigational new drug (IND) or research study procedure, there are risks that are not known that may be serious and may even cause death. The most up to date information regarding efficacy, safety, and benefit-risk assessment for cipaglucosidase alfa/miglustat can be found in the current Investigator's Brochure.

Cipaglucosidase alfa/miglustat has proven overall to be generally safe and relatively well tolerated. Alternative treatments provide initial benefit to patients with Pompe disease. The magnitude and duration of therapeutic response with continuing therapy varies among individual subjects and, at best, may offer improvement in measures of muscle function, strength, and respiratory function for a finite duration, ie, 2 to 3 years in most subjects, followed by a slow decline in these parameters. These alternative treatments may themselves be associated with significant risks. A monthly review for safety signals is part of routine pharmacovigilance.

The strength of the current benefit-risk analysis is based on the safety pool of data from a variety of sources (clinical study, literature, and independent registries) and in various geographies (eg, EU, Australia, and US) while the mean duration of treatment is approaching 36 months.

Weakness of the data is primarily based on the small number of subjects in the clinical study described. There are no specific studies that target specific subpopulations of patients such as elderly, or subpopulations. Uncertainties exist over the long-term safety profile.

Study participants may not experience any benefit from participating in this study. However, potential benefits include stabilization or improvement in the signs and symptoms of Pompe disease and the positive health effects of regular surveillance by a physician. In addition, study participation provides the opportunity to contribute data relevant and necessary for continued advancement in the treatment of Pompe disease. In light of the progressive nature of Pompe disease and the benefits observed in adults with LOPD to date, the potential benefits justify the risks and inconveniences of clinical trial participation. The sponsor acknowledges that these inconveniences include frequent travel to the study site with associated impact on attendance at work and/or school; the discomfort of study procedures, such as blood draws; and the need to

follow other study requirements, such as adequate birth control for females of child-bearing potential. However, the sponsor has made efforts to limit this impact by allowing for at-home administration of study medication (if permitted locally and deemed clinically appropriate based on criteria outlined in the protocol) and minimizing the number of visits with full study assessments. Finally, study participants are informed at the time of consent that if at any time they do not wish to continue with the study, eg if the risks or inconveniences become too onerous, they may withdraw without any adverse impact on their ongoing care by their physician.

Refer to the current IB for updated information.

## **6.7. Study Population**

This is an open-label extension study for adult subjects with LOPD who completed Study ATB200-03. For this amendment, subjects may continue in this study until commercial cipaglucosidase alfa/miglustat becomes available in their country as a treatment for Pompe patients.

## 7. STUDY OBJECTIVES

The final analysis will be performed for the final CSR based on a data cutoff date of 31 December 2024 with the study objectives below. The study objectives upon approval of this amendment are presented in [Appendix 1](#), Section [7](#).

### 7.1. Primary Objective

The primary objective of this study is to assess the long-term safety and tolerability of cipaglucosidase alfa/miglustat co-administration.

### 7.2. Secondary Objectives

The secondary objectives of this study are as follows:

- to assess the long-term efficacy of cipaglucosidase alfa/miglustat co-administration on ambulatory function, as measured by the 6-minute walk test (6MWT)
- to assess the long-term efficacy cipaglucosidase alfa/miglustat co-administration on pulmonary function, as measured by sitting forced vital capacity (FVC) (% predicted)
- to assess the long-term efficacy of cipaglucosidase alfa/miglustat co-administration on muscle strength
- to assess the long-term efficacy of cipaglucosidase alfa/miglustat co-administration on health-related patient-reported outcomes
- to assess the long-term efficacy of cipaglucosidase alfa/miglustat co-administration on motor function
- to assess the long-term efficacy of cipaglucosidase alfa/miglustat co-administration on overall clinical impression, as assessed by both physician and subject
- to assess the long-term efficacy of cipaglucosidase alfa/miglustat co-administration on measures of pulmonary function other than FVC (% predicted)
- to assess the long-term effect of cipaglucosidase alfa/miglustat co-administration on biomarkers of muscle injury and disease substrate
- to assess the immunogenicity of cipaglucosidase alfa/miglustat co-administration
- to characterize the pharmacokinetics of cipaglucosidase alfa and miglustat using plasma total GAA protein level by signature peptide and plasma miglustat concentration assays in subjects at sites in Japan only

## 8. INVESTIGATIONAL PLAN

### 8.1. Study Design

This is a multicenter, international, open-label extension study of cipaglucosidase alfa/miglustat in adult subjects with LOPD who completed Study ATB200-03.

The purpose of this amendment is to continue collecting long-term safety and efficacy data on LOPD subjects treated with cipaglucosidase alfa/miglustat while decreasing some of the burden on those subjects taking part, and continuing to provide treatment where regulatory approval has not yet been granted or the product is not yet commercially available. Subjects may continue in this study until commercial cipaglucosidase alfa/miglustat becomes available in their country as a treatment for Pompe patients. The final analysis will be performed for the final CSR based on a data cutoff date of 31 December 2024. Upon approval of this amendment, any subjects continuing in the study will follow the updated Schedule of Assessments in [Table 10](#).

For subjects who participated in Study ATB200-03, the first infusion visit in this study should be scheduled approximately 2 weeks after the last visit in Study ATB200-03 in an effort to ensure continued administration of study drug on the same schedule with no gap between studies. Infusion visits for administration of study drug will be scheduled every 2 weeks throughout the study; assessments (eg, clinical laboratory tests) for monitoring of initial safety will be performed at these infusion visits for the first 6 weeks of the study. During the conduct of the study, the SARS-CoV-2 (COVID-19) pandemic emerged and impeded the conduct of site visits and laboratory testing due to quarantines, travel restrictions, and risk of infection. With the intention of maintaining regular infusions, home infusions will be allowed prior to completing Week 12 wherever possible for subjects who may be eligible (see Section [12.2.2](#)). Study visits that include efficacy, safety, and other assessments will be scheduled approximately every 3 months for the first 6 months, then every 6 months thereafter. These visits may occur over 2 days, provided all study assessments and procedures (with the exception of PK sample collection) are performed before administration of study drug. If a visit was missed due to COVID-19-related quarantines, travel restrictions, and risk of infection, it should be recorded as such in the Interactive Response Technology (IRT) system and electronic data capture (EDC) system. A reason for the missed visit should be entered into the EDC as COVID-19 related. The relevant institutional review boards (IRBs), independent ethics committees (IECs), and REBs should be notified of any deviations from the protocol. If infusions were missed near the scheduled assessments at Week 12, Week 26, or at any of the study visits scheduled every 26 weeks after Week 26, it should be communicated with Amicus on a case-by-case basis to determine whether catch-up infusions are needed and how many catch-up infusions are needed prior to the study assessments.

Efficacy assessments (ie, functional assessments) include evaluation of ambulatory function (6MWT), motor function tests (Gait, Stairs, Gowers' maneuver, and Chair [GSGC] test and timed up and go [TUG] test), muscle strength (manual muscle testing and quantitative muscle testing), and pulmonary function tests (FVC, slow vital capacity [SVC], maximal inspiratory pressure [MIP], maximal expiratory pressure [MEP], and sniff nasal inspiratory pressure [SNIP]). Patient-reported outcomes include Rasch-built Pompe-specific Activity (R-PAct) Scale, EuroQol 5 Dimensions-5 Levels Instrument (EQ-5D-5L), Patient-reported Outcomes Measurement Information System (PROMIS®) instruments for physical function, fatigue,

dyspnea, and upper extremity, and Subject's Global Impression of Change (SGIC). The Physician's Global Impression of Change (PGIC) will also be performed. Pharmacodynamic assessments include measurement of biomarkers of muscle injury (CK) and disease substrate (urinary Hex4). Blood samples for PK assessment of total GAA protein and miglustat concentration in plasma will be collected from subjects at sites in Japan only. Safety assessments include monitoring of AEs, including IARs, clinical laboratory tests (chemistry, hematology, and urinalysis), vital signs, physical examinations including weight, ECGs, and immunogenicity. Concomitant medications and nondrug therapies will also be recorded.

For subjects continuing in the study after approval of this amendment, updated efficacy and safety assessments are provided in [Appendix 1](#), Section 8.1.

## **8.2. Duration of Study**

The study will consist of a treatment period that lasts until one of the following conditions apply:

- the product is approved and commercialized for use in the investigational study population, or
- cipaglucosidase alfa/miglustat is rejected by the regulatory authority in the subject's local country as an approved treatment for Pompe disease, or
- the sponsor decides to continue to provide cipaglucosidase alfa/miglustat via a post-trial access mechanism, or
- the subject is withdrawn or withdraws consent, or
- the sponsor decides to end the study.

## **8.3. Criteria for Termination of the Study**

The study may be terminated by the sponsor if there is evidence suggesting that safety risks associated with cipaglucosidase alfa/miglustat treatment outweigh the potential benefits.

## **8.4. Definition of the End of Study**

End of study is defined as the date of the last subject's last visit. The final analysis will be performed for the final CSR based on a data cutoff date of 31 December 2024. Any data collected after this date will be provided as an addendum to the final CSR when all subjects have completed the study or have been withdrawn from the study. Upon approval of this amendment, subjects who remain in the study will follow the Schedule of Assessments in [Appendix 1](#) ([Table 10](#)).

## **8.5. Definition of Study Completer**

A study completer is defined as a subject who has fulfilled both of the following requirements:

- completion of study treatment, defined as continuing to receive treatment as a participant in the ATB200-07 study until the study ends or until the subject transitions to locally approved and commercially available cipaglucosidase alfa/miglustat or another post-trial access mechanism

## **8.6. Discussion of Study Design, Including Choice of Control Groups**

This is an open-label extension study to assess the long-term safety of cipaglucosidase alfa/miglustat and has no control group. Although efficacy will be assessed, it is not a primary objective.

## **9. SUBJECT SELECTION AND WITHDRAWAL CRITERIA**

### **9.1. Number of Subjects**

The maximum sample size for this study is based on the number of subjects who complete Study ATB200-03, estimated to be approximately 110 subjects at up to approximately 59 sites globally.

### **9.2. Eligibility Criteria**

#### **9.2.1. Subjects Who Participated in Study ATB200-03**

Subjects who participated in Study ATB200-03 must meet all of the inclusion criteria and none of the exclusion criteria to be eligible to participate in the study.

##### **9.2.1.1. Inclusion Criteria**

1. Subject must provide signed informed consent prior to any study-related procedures being performed. If the subject is under 20 years of age, the subject must provide written informed consent. In Japan, the subject's parental guardian (or legal representative) must also sign the informed consent form.
2. Subjects must have completed Study ATB200-03.

Note: Subjects who were forced to withdraw from Study ATB200-03 for a logistical reason not related to the efficacy or safety of cipaglucosidase alfa/miglustat (eg, hospitalization for a car accident, COVID-19 pandemic, or emergency surgery) and which resulted in several consecutive missed doses may be eligible to participate in this study upon approval by the Amicus medical monitor.

3. Female subjects of childbearing potential and male subjects must agree to use medically accepted methods of contraception during the study and for 90 days after the last dose of study drug.

##### **9.2.1.2. Exclusion Criteria**

1. Subject plans to receive gene therapy or participate in another interventional study for Pompe disease.
2. Subject has a hypersensitivity to any of the excipients in cipaglucosidase alfa or miglustat, or has a medical condition or any other extenuating circumstance that may, in the opinion of the investigator or medical monitor, pose an undue safety risk to the subject or may compromise his/her ability to comply with or adversely impact protocol requirements. This includes clinical depression (as diagnosed by a psychiatrist or other mental health professional) with uncontrolled or poorly controlled symptoms.
3. Subject, if female, is pregnant or breastfeeding.
4. Subject, whether male or female, is planning to conceive a child during the study.

### **9.3. Withdrawal Criteria**

Subjects may withdraw or be withdrawn from the study for any reason, including, but not limited to, the following:

- at their own request
- if, in the investigator's opinion, continuation in the study would be detrimental to the subject's well-being

Note: Subjects with serious adverse events (SAEs) of anaphylaxis to cipaglucosidase alfa must be withdrawn from the study.

- if, in the investigator's opinion, there is a lack of efficacy for the subject
- persistent noncompliance with study requirements, such as failure to comply with the study visit schedule, in the judgment of the investigator and/or medical monitor
- persistent noncompliance with study drug or failure to return to the study site for infusion visits, in the judgment of the investigator and/or medical monitor
- inability to contact subject (ie, subject is lost to follow-up)
- pregnancy (female subjects)
- planning to conceive a child (male or female subjects)
- sponsor decision to terminate the study

In all cases, the reason for withdrawal and the date of withdrawal must be recorded in the electronic case report form (eCRF) and in the subject's medical records.

Subjects who withdraw will be requested to complete the Early Termination Visit. The investigator will make every effort to contact withdrawing subjects and schedule the early termination assessments. Upon study completion or subject discontinuation, subjects who are confirmed positive for anti-rhGAA antibodies will complete follow-up immunological testing for up to 12 months after the last dose of study drug (ie, at 6 months and 12 months) or until they begin treatment with an investigational therapy or an ERT that is approved by the local health authority and is commercially available (see [12.2.6](#)).

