#### **13.1.2. Serious Adverse Events**

A SAE is any AE that

- results in death
- is life-threatening
  - An AE, in the view of either the investigator or Amicus, that places the subject at immediate risk of death. It does not include an AE that, had it occurred in a more serious form, might have caused death.

- requires inpatient hospitalization or prolongs existing hospitalization
  - Hospitalization signifies that the subject has been admitted, regardless of duration, for observation and/or treatment that would not have been appropriate in a physician's office or outpatient setting.
  - Hospitalizations for elective or preplanned treatment of a pre-existing condition do not have to be reported as SAEs, provided that
    - the condition is documented in the subject's medical history and has not worsened since the informed consent form (ICF) was first signed, and
    - the planned procedure is documented in the subject's eCRF at the Baseline Visit.

Note: Outpatient procedures performed in a hospital do not qualify as an SAE.

- Emergency room/department or outpatient treatments that do not result in admission do not have to be reported as an SAE, unless another SAE criterion is met.
  - Events assessed and treated in these circumstances should be captured as AEs.
  - Hospitalizations solely based on logistics (eg, subject is admitted due to limited hospital accessibility for what would otherwise be an outpatient procedure) do not have to be reported as SAEs.
    - These hospitalizations should be clearly defined as such in the subject's source record.
- results in persistent or significant incapacity or substantial disruption of the ability to conduct normal life functions, as decided by the investigator
- is a congenital anomaly/birth defect

An important medical event that may not result in one of the above-mentioned serious outcomes may be considered an SAE when, based on appropriate medical judgment, it may jeopardize the subject and may require medical or surgical intervention to prevent one of the serious outcomes. Examples of such medical events include allergic bronchospasm requiring intensive treatment in an emergency room or at home, blood dyscrasias or convulsions that do not result in inpatient hospitalization, or development of drug dependency or drug abuse.

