### 13.1.3. Infusion-associated Reactions

An IAR is defined as a disorder characterized by 1 or more adverse reaction(s) to the infusion of pharmacological or biological substances. These reactions are classified into 2 major subtypes, early and late, according to the time interval between the infusion and the onset of an infusion-related AE.

The reactions are divided into 5 severity grades as follows:

1. Mild (requires observation only); for example, transient flushing or rash
2. Moderate (minimal, usually oral, intervention suffices); for example, urticaria/myalgia/drug fever
3. Severe (vital organ involved yet not in a life-threatening manner; usually requires parenteral medication); for example, bronchospasm/angioedema/hypotension
4. Life threatening (multisystem involvement of vital organs, urgent and critical care required); for example, systemic anaphylactic reaction
5. Death

Early IARs is any symptom or sign occurring during or within 24 hours of completion of the infusion and deemed a drug-related AE by the investigator, unless an alternative obvious explanation exists, eg, mechanical fall. Early IARs commonly involve 1 or more of the following systems: skin (urticaria and erythema), eyes (conjunctivitis), nasopharynx (rhinorrhea, rhinitis), bronchopulmonary tissues (wheezing, bronchospasm), and gastrointestinal tract (diarrhea, vomiting).

Late IAR is any symptom or sign occurring more than 24 hours (usually 1 to 3 days) after completion of the infusion that, in the investigator's opinion, fits the clinical description of a symptom or sign associated with an IAR. The most common symptoms of late IARs are pruritic skin eruptions, fever, malaise, and polyarthralgia.

Note: The list of IAR symptoms provided in [Table 9](#) is not comprehensive. It is meant to serve as a guideline to the investigators to report and manage IAR as AE. [Table 9](#) also provides a guideline for management of IARs and anaphylaxis (see also [Appendix 2](#)). The guideline is intended for sites that do not have such procedures in place. It is at the investigator's discretion to follow the guidelines or implement treatment protocol that their center is accustomed to following.

When an IAR occurs, it is important to report and indicate in the eCRF all AEs that are associated with the IAR. All available details of the events observed with an IAR are necessary to assess the evolution of the AEs after premedication for subsequent infusions.

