In the event that a subject experiences an IAR, the subject should be premedicated for subsequent infusions with antihistamines, steroids, and/or acetaminophen, infusion rate adjustments, or other steps taken. If these measures are not successful, the investigator/designee should contact the medical monitor for guidance. The premedications should be continued for all remaining infusions.

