**Table 9: Guidelines for Management of Early Infusion-associated Reactions (Continued)**

Severity	Symptoms (such as, but not restricted to)	Management Guidelines
Severe reaction, anaphylaxis, or anaphylactoid reactions	Chest pain Generalized urticarial/angioedema Symptomatic hypotension (subject feeling faint, paleness) Hoarseness of voice/laryngeal edema Bronchospasm	
** STOP INFUSION **
 
Activate emergency response and immediately contact investigator.
 
For chest pain and symptomatic hypotension, initiate emergency procedures.
 
Administer high-flow oxygen or intubate and mechanically ventilate as appropriate.
 
Give IM adrenaline 300 mcg EpiPen into thigh (avoid buttock). If no response, repeat dose in 5 minutes. Prepare infusion of adrenaline 3 mg/50 mL NS (60 µg/mL), if needed.
 
Give IV fluids 10- to 20-mL/kg fluid bolus on direction of investigator/designee.
 
Give IV antihistamines (promethazine 25 to 50 mg in 10 mL WFI over 2 to 3 minutes).
 
Give IV steroids (hydrocortisone 100- to 500-mg bolus IV injection; dilute in 10 mL NS for doses between 100 and 500 mg) and infuse over 2 minutes.
 
Give nebulized beta-2 agonists with high-flow oxygen on direction of investigator/designee.
 
Administer other treatments and/or transfer patient to hospital/ICU as recommended by investigator/designee.
 
Observe subject for a minimum of 24 hours after resolution of the event.
 
If deemed appropriate by investigator/designee, study drug infusion can be re-initiated 7 to 14 days with premedications and at the 4-hour duration.
 
Record all details. Report AE, if applicable.

Abbreviations: AE = adverse event; GAA = human acid  $\alpha$ -glucosidase; ICU = intensive care unit; IgE = immunoglobulin E; IM = intramuscular; IV = intravenous; NS = normal saline; WFI = water for injection  
Source: [Vogel 2010](#); [Sampson, Muñoz-Furlong et al. 2006](#)

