### **13.3. Reporting Requirements for Serious Adverse Events**

If an AE is serious (as defined in Section 13.1.2), the investigator must submit an SAE report form at the time the SAE is identified. All SAEs must be immediately reported by the investigator to Amicus or Amicus' designee, but no later than 24 hours after any study site personnel is aware of the event. Serious adverse event report forms must be faxed to the designated safety fax number ([contact]) or sent via email to [contact]. All supporting documentation available at the time of reporting, with all subject identifiers redacted in accordance with local requirements, must be included in the fax along with the SAE report form.

The initial report must be completed as soon as possible. All known details of the SAE and an assessment of the causal relationship between the event and study drug, or study procedure should be included in the initial report. All information not available at the time of the initial report (eg, event end date, discharge summary, or results of diagnostic procedures/evaluations related to the event) must be provided in a follow-up report. Follow-up information must be reported using the designated fax number within 24 hours of receipt at study sites.

Every attempt should be made to describe events in terms of a diagnosis. If a clear diagnosis has been made, individual signs and symptoms should not be recorded unless they represent atypical or extreme manifestations of the diagnosis, in which case they should be reported as separate events. If a clear diagnosis cannot be established, each sign and symptom must be recorded individually.

Study endpoints that meet SAE criteria (as per Section 13.1.2) must also be immediately reported by the investigator to Amicus or Amicus' representative but no later than 24 hours after any study site personnel is aware of the event.

If a nonserious event becomes serious, the event must be reported as described above.

If the investigator becomes aware of an SAE in a subject or receives an unsolicited report of an SAE from a subject more than 30 days after the last treatment, and considers the event possibly, probably, or definitely related to previous study treatment, he or she should contact the Amicus medical monitor to determine how the SAE should be documented and reported.

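### The Table 9 restart option for anaphylaxis does not exclude the serious cases that Section 9.3 says must be withdrawn

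*Protocol*

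**What the plan says.** **The rule.** Protocol Section 9.3 (Withdrawal Criteria) states: "Subjects with serious adverse events (SAEs) of anaphylaxis to cipaglucosidase alfa must be withdrawn from the study". The sentence is a note under the bullet on continuation being detrimental to the subject in the investigator's opinion.

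**The guideline.** Section 13.1.3 introduces Table 9 as guidance on managing IARs and anaphylaxis. Its last row is labelled "Severe reaction, anaphylaxis, or anaphylactoid reactions". After the acute measures, that row says: "If deemed appropriate by investigator/designee, study drug infusion can be re-initiated 7 to 14 days with premedications and at the 4-hour duration".

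**The status of the guideline.** Section 13.1.3 intends Table 9 for sites without procedures of their own. Investigators have "discretion to follow the guidelines or implement treatment protocol that their center is accustomed to following".

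**The paragraph before Table 9.** "In the event that a subject experiences an IAR, the subject should be premedicated for subsequent infusions". The medical monitor is brought in only if premedication, rate changes or other steps do not work.

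**Amendment 3.** Appendix 1 refers back to the main body for Sections 9 and 13, so both texts still apply to subjects who continue. Table 10 keeps dosing at every 2 weeks.

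**The concern.** Someone handling a reaction will look at Table 9. Its most severe row names anaphylaxis and ends with a route back to dosing, on the judgement of the investigator or designee alone. For an SAE of anaphylaxis to cipaglucosidase alfa, Section 9.3 has already decided the matter: the subject leaves the study. Neither the row, the table footnote nor Section 13.1.3 says so.

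The sites most likely to use Table 9 as written are those with no procedure of their own, which are the sites it was written for. What is at stake is re-exposure of a subject whom the protocol means to withdraw.

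**Working it through.** The plan gives no figure to reproduce here. The check is mainly a comparison of texts, with one short piece of arithmetic on the safeguard.

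**1. Do the two texts cover the same event?**

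- Section 13.1.3, severity grade 4: "Life threatening (multisystem involvement of vital organs, urgent and critical care required); for example, systemic anaphylactic reaction". Systemic anaphylaxis is thus the protocol's own example of a life-threatening IAR.
- Section 13.1.2 makes a life-threatening event an SAE, defined as "An AE, in the view of either the investigator or Amicus, that places the subject at immediate risk of death".
- So a life-threatening systemic anaphylactic reaction to cipaglucosidase alfa is an SAE of anaphylaxis, and Section 9.3 applies.
- The same reaction falls in the Table 9 row by its label, so the restart line applies too.

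A second route to seriousness points the same way. The row calls for at least 24 hours of observation after resolution and allows transfer to hospital or intensive care. Section 13.1.2 counts an inpatient admission of any length, for observation or treatment unsuited to an outpatient setting, as serious. Anaphylaxis managed as the row describes is therefore likely, though not certain, to be an SAE.

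**2. Does anything in or near Table 9 exclude these cases?**

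| Text | Excludes SAEs of anaphylaxis? | Points to Section 9.3? |
|---|---|---|
| Table 9, severe/anaphylaxis row | No | No |
| Table 9 footnote | No | No |
| Section 13.1.3, premedication paragraph | No | No |
| Section 12.3.12, IgE draws after anaphylaxis (the third just before the next dose) | No | No |

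**3. Do other provisions close the gap?**

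- Section 13.3 requires an SAE report "no later than 24 hours after any study site personnel is aware of the event". This tells the sponsor but does not hold the restart.
- Section 16.3.4 bars dosing deviations that may significantly affect safety. It is a general prohibition.
- Section 16.3.5 requires staff to be informed about the protocol, which includes Section 9.3.
- Section 12.2.2 excludes from home infusion subjects with a moderate or severe IAR in this study, or any history of recurrent severe or life-threatening IARs including anaphylaxis. It governs where dosing takes place, not whether it continues.

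All four reduce the risk. None removes or conditions the restart line.

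**4. How much time does the SAE report give the sponsor?**

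Inputs: reporting limit 24 hours = 1 day (Section 13.3); restart at day 7 to day 14 (Table 9). Assumption: both clocks start at the reaction.

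Time to act = restart day − reporting limit:

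- earliest restart: 7 − 1 = 6 days
- latest restart: 14 − 1 = 13 days

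The assumption is needed because Table 9 does not say when its 7 to 14 days begin, and the SAE clock runs from site awareness. Later awareness shortens the interval. Counting the 7 to 14 days from resolution lengthens it.

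**The case against.** The strongest reply is that the texts do not give opposing instructions. Section 9.3 is mandatory, while Table 9 only permits a restart where it is judged appropriate. A permission of that kind cannot override a requirement, so a site that reads both withdraws the subject. This stands, and it is why the point is a missing exclusion and not a contradiction.

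The restart line also has proper uses. Grade 3 severe reactions are by definition not life-threatening, and Section 9.3 does not reach them. Some anaphylaxis can meet the Appendix 2 criteria without being life-threatening, for example skin involvement with persistent gastrointestinal symptoms, and may not be classed as an SAE. This stands too: the line should be limited, not deleted.

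The premedication paragraph is weaker evidence. A withdrawn subject has no later infusions, so that paragraph does not itself authorise re-dosing. A cross-reference there is helpful but not essential.

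Finally, harm would need a site to overlook a mandatory rule and the sponsor then to miss acting on a reported SAE. Section 6.6 describes the IARs as mild to moderate, with none life-threatening or fatal to date. That keeps the probability low. It does not make the restart line correct for the cases it wrongly includes, and Table 9 is aimed at the sites most likely to follow it literally.

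**Conclusion.** The concern holds. For SAEs of anaphylaxis to cipaglucosidase alfa, Table 9 offers a restart that Section 9.3 rules out, and nothing in or near the table says so. It should be fixed, as a minor patient-safety consistency point.

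Its reach is narrow. It concerns only those SAEs, and no event rate is claimed because the documents give none. The 6 to 13 days available to the sponsor is a mitigation that rests on both clocks starting at the reaction; the conclusion does not depend on it. Sample size, endpoints and analyses are unaffected.

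**What to change.** Add one sentence to the restart line in the severe/anaphylaxis row of Table 9:

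> *Does not apply to SAEs of anaphylaxis to cipaglucosidase alfa: do not re-initiate study drug; withdraw the subject per Section 9.3.*

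Add *see Section 9.3* to the premedication paragraph before Table 9. Leave the rest of the row unchanged, so that a restart remains available after severe non-anaphylactic reactions and after anaphylaxis not classed as an SAE. As an optional extra, the IgE sampling text in Section 12.3.12 could say that the third draw applies only where dosing continues.

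The cost is close to nothing: one sentence and one cross-reference, with no new visit, test or dosing rule and no change to Section 9.3. Section 16.3.4 already provides for a clarification memo to sites and ethics committees ahead of an amendment. That can serve as the interim step, with the wording carried into the next amendment.
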